### Cellular response

For Elispot and for each peptide: n, median, quartile range, min, max of actual values, percentage of responders above a predefined threshold (see section 6.4) and corresponding 95% CI will be tabulated.

Graphical presentations will be provided displaying dots for the subject values and including the median and the percentage of responders. In the graphs the actual values will be shown and the LLOQ cut-off will be visualized, the values below LLOQ will be visualized with the value imputed as described in section 6.3.

Reverse distribution curves of the actual values will be provided.

In the graphs, original values will be displayed on the  $\log_{10}$  scale.

### ICS

#### 1) T cells: CD4+, CD8+

*Antigen: Combined pools and separated pools*

Cytokine counts: Marginal, Boolean AND (co-expression) counts, Boolean OR (and/or)

For CD4+ and CD8+ and for each antigen (combined and separated pools): n, median, quartile range, min, max, percentage of responders (see section 6.4) and corresponding 95% CI will be tabulated for each available cytokine count listed below.

Cytokine (ISSCAT)	Description
CD154+	Marginal
GzB+	Marginal
ICOS+	Marginal
IFNg+	Marginal
IL2+	Marginal
IL17a+	Marginal
IL4+	Marginal
TNFa+	Marginal
IFNg+/IL2+	Boolean AND (co-expression)
IFNg+/IL2+/TNFa+	Boolean AND (co-expression)
IFNg+/TNFa+	Boolean AND (co-expression)
IL2+/TNFa+	Boolean AND (co-expression)
IFNg+ or IL2+	Boolean OR (and/or)
IFNg+ or IL2+ or TNFa+	Boolean OR (and/or)

Graphical presentations will be provided displaying dots for the subject values and including the median and the percentage of responders. In the graphs the actual values will be shown and the LLOQ cut-off will be visualized, the values below LLOQ will be visualized with the value imputed as LLOQ/2.

In the graphs, original values will be displayed on the  $\log_{10}$  scale.

The technical details for the calculation of the cytokine background adjusted percentages to be displayed in the above described outputs will be outlined in the DPS.

Additional timepoints between and tests within one of the above listed assays may be investigated for exploratory purposes. These data and data from timepoints belonging to the long term extension part of the study will be analyzed using the approaches described above.

#### **6.4. Handling of Missing and/or Invalid Immune Response Data**

Analysis will be carried out on the available data, no imputation will be done for missing samples.

BAMA and ICS unreliable values should be excluded from the analysis: those records will be flagged in the SDTM dataset.

LLOQs by assay/test are listed in Table 1. Values below LLOQ or LOD will be handled as follows:

- Calculation of Geomean (humoral response) and median (cellular response):
  - o values < LLOQ are imputed =LLOQ/2
  - o values = LOD are not imputed unless no LLOQ is available. In that case LOD will handled similarly to LLOQ (see ADCP)
- Calculation of fold increases from baseline:
  - o values <LLOQ are imputed =LLOQ
  - o values =LOD are imputed = LLOQ when LLOQ is available

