11.4. Immunogenicity Analyses

No formal hypothesis on immunogenicity will be tested. The analysis of immunogenicity will be done on the immunogenicity and per-protocol populations as defined in Section 11.1.

Descriptive statistics (actual values and changes from reference) will be calculated for continuous immunologic parameters at all time points. Graphical representations of changes in immunologic parameters will be made as applicable. Differences between groups at a specific time point will be tested for exploratory purposes by a 2-sample t-test if the data appear to be normally distributed. If not, the non-parametric Wilcoxon rank sum test will be used. If portions of the measurements are censored below the assay quantification limit, the Gehan-Wilcoxon test will be employed. All statistical tests will be two-sided and will be considered statistically significant if $p<0.05$.

Frequency tabulations will be calculated for discrete (qualitative) immunologic parameters at all time points. Significant differences between groups will be determined by a 2-sided Fisher's exact test.

Magnitude and breadth of (neutralizing) antibody responses will be explored graphically through the generation of individual magnitude-breadth (M-B) curves. The area under the M-B curve (AUC) provides an overall summary of the M-B profile. The AUCs will be compared between groups using the Wilcoxon-Mann-Whitney test.

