#### Humoral assays

For all the humoral assays the immune response values will be  $\log_{10}$ -transformed before any further handling. The  $\log_{10}$ -transformed values will be used throughout the analysis. In the graphs, original values will be displayed on the  $\log_{10}$  scale.

For each assay and at each time point geometric mean of actual values, geometric mean increases and percentage of responders, all with corresponding 95% CIs will be provided in the tables. The definition of responders is defined in

section 6.4. for each assay. Graphical presentations will be provided displaying dots for the subject values and including the geometric mean and the percentage of responders. If available, baseline values will be summarized pooling the 8 groups and will be displayed on the left of each graph. Week 28 and Week 52 timepoints will be plotted next to each other for each group, a line will link the geometric mean (or the median) of the 2 different time points within the same group.

In the graphs the actual values will be shown and the LLOQ cut-off will be visualized, the values below LLOQ or below LOD will be visualized with the value imputed as described in section 6.3.

Vaccine durability will be shown by linear plots of the GM/median for each group.

Reverse distribution curves of the actual values will be provided for selected assays.

For BAMA the median will be reported instead of the geometric mean. Cumulative number of responses across the IgG/antigen classes will be tabulated.

Magnitude-breadth (MB) plots for the BAMA assay will be provided at each timepoint to explore the magnitude (MFI of IgG3 and of IgG breadth binding antibodies) and breadth (number antigens at a given MFI) of each individual serum sample assayed. MB curves will show, for each possible MFI threshold, the fraction of antigens with MFI greater than this threshold.

The group-specific curve obtained as the average MB across all subjects in that group will be displayed. The AUC-MB is calculated as the average of the MFI over the panel of antigens.

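### If about half or more LTE titres fall below LLOQ, setting them to LLOQ/2 would lift the geometric mean and make waning look like a plateau; the SAP plans no sensitivity analysis

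*SAP*

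**What the plan says.** SAP 6.4 gives the rule for humoral geometric means: "values < LLOQ are imputed =LLOQ/2". There is one exception: "values = LOD are not imputed unless no LLOQ is available". For fold increases the substituted value is LLOQ itself, a floor twice as high.

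SAP 6.3 (Humoral assays) works on the log10 scale, where the "transformed values will be used throughout the analysis". It promises that, per assay and time point, "geometric mean of actual values, geometric mean increases and percentage of responders, all with corresponding 95% CIs will be provided in the tables". On persistence it says "Vaccine durability will be shown by linear plots of the GM/median for each group". The closing paragraph of SAP 6.3 extends this to the LTE: "data from timepoints belonging to the long term extension part of the study will be analyzed using the approaches described above".

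Protocol 11.4 anticipates censoring ("If portions of the measurements are censored below the assay quantification limit") and then names the Gehan-Wilcoxon test, for comparisons between groups only. The SAP does not repeat that test. It plans neither a censored-data estimate of the geometric mean nor a sensitivity analysis of the substitution.

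The table in SAP 6.5 lists gp140 ELISA LLOQs of 625 (Clade A, Clade C Con C), 156.25 (Clade B, Clade C C97ZA.012) and 78.125 EU/mL (Mos1), and says that final values may differ.

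**The concern.** Durability in Groups 1 and 2 up to Week 336 is what the LTE is for (Protocol 2.1, exploratory objective). It will be read from lines of geometric means or medians over time. When titres wane past the LLOQ, substitution replaces a spreading lower tail by a single value. Two things follow. The mean stops tracking the decline, and the sample SD that sets the CI width shrinks. A line that flattens for this reason would be read as a persistent response, with a CI that looks precise. Because ELISA LLOQs differ 8-fold (625/78.125), the flattening would also start at different titres for different antigens.

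**Working it through.** **Inputs.** SD 0.6 log10 and 45 evaluable subjects per group (Protocol 11.2); the LLOQ/2 rule (SAP 6.4); LLOQs and LODs (SAP 6.5). Assumptions not in the documents: normal log10 titres, the same SD over time, a one-sample t interval, and the share p below LLOQ, which is varied.

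**Planning figure first.** Detectable log10 difference = (1.960 + 0.842) × 0.6 × √(2/n). For n = 45, 90 and 135 this gives 0.354, 0.251 and 0.205, that is 2.26-, 1.78- and 1.60-fold. The protocol's 2.3, 1.8 and 1.6 reproduce.

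**Bias of the geometric mean (GM).** Put the true log10 mean at 0 and the LLOQ at its p-th percentile, L = 0.6 × z_p. The mean of the values below L is −0.6 × φ(z_p)/p. Then

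bias = p × [(L − 0.301) + 0.6 × φ(z_p)/p].

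- p = 50%: L = 0, mean below −0.479; bias = 0.5 × (−0.301 + 0.479) = 0.089, or 1.23-fold.
- p = 70%: L = 0.315, mean below −0.298; bias = 0.7 × (0.315 − 0.301 + 0.298) = 0.218, or 1.65-fold.

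**Coverage of the 95% CI** (40,000 simulated samples per cell, n = 45):

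| Below LLOQ | Reported/true GM | Coverage |
|---|---|---|
| 20% | 1.02 | 95% |
| 30% | 1.06 | 94–95% |
| 40% | 1.12 | 92% |
| 50% | 1.23 | 80% |
| 60% | 1.39 | 37% |
| 70% | 1.65 | about 0% |

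Nearly all misses at 50% and above have the whole interval above the truth. The LTE set may well be smaller than 45 per group: at 50% below LLOQ, coverage is 87% with n = 30 and 89% with n = 25. At 70% it still collapses (0.7% and 3.1%).

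**Dependence on SD.** At p = 50% the bias is zero when 0.301 = 2 × 0.3989 × SD, so SD = 0.38. With n = 45 the ratio (and coverage) is 0.93 (88%) at SD 0.3, 1.02 (95%) at 0.4, 1.12 (90%) at 0.5 and 1.47 (54%) at 0.8.

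**Illustrative waning**, true GM falling from 2000 to 200 EU/mL (assumed titres, SD 0.6):

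| LLOQ | Below LLOQ, start / end | Shown GM | Shown fall |
|---|---|---|---|
| 625 | 20% / 80% | 2031 to 422 | 4.8-fold |
| 156.25 | 3% / 43% | 1990 to 230 | 8.7-fold |
| 78.125 | 1% / 25% | 1996 to 206 | 9.7-fold |

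At LLOQ 625 the shown fall is 5.5-fold with SD 0.4 and 4.4-fold with SD 0.8. At the two lower LLOQs with SD 0.4 it is 10.2- and 10.3-fold, so durability is not overstated there.

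**LOD exception.** IgG1 and IgG2 have LOD 4 against LLOQs of 12.3 and 28.7. If values at or below LOD are kept at 4, 50% below LLOQ gives 1.12 and 1.11 with about 92% coverage; 70% gives 1.40 and 1.31 with 32% and 64%.

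**Left-censored normal likelihood**, same setting, 1,500 samples: at 30, 50 and 70% below LLOQ, the ratio is 0.99, 0.99 and 0.98 and coverage 95.9, 94.9 and 94.0%.

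**The case against.** A reader might infer that the plan will overstate durability. The documents do not support that. They give no expected share below LLOQ; up to about 30% the effect is negligible; and 0.6 is a sample-size planning value, not an LTE estimate. This stands.

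A reader might also take LLOQ/2 as a hard floor for every assay. It is not: the LOD exception lets IgG1-4 values sit below it. BAMA and the cellular assays use medians, which the substitution leaves alone until about half the values are below LLOQ. Protocol 9.2.2 leaves the LTE assay list open; it names the binding antibody assay and ELISPOT as possibilities. The 4.8-fold example applies to two of five ELISA antigens, and the SAP plans no comparison of geometric means across antigens. This stands too.

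Nor do the protocol and SAP contradict each other over Gehan-Wilcoxon: that is an exploratory test between groups, not an estimate.

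Much of the censoring will be visible. SAP 6.3 provides responder percentages with CIs, individual values, an LLOQ line on graphs and, for selected assays, reverse distribution curves. At SD 0.6 the substituted mean itself drops to 0.98, 0.80 and 0.67 of LLOQ at 60, 70 and 80% below LLOQ, which should warn a careful reader. These displays help, but they do not correct the mean, its CI or the durability line, and the SAP does not expressly put the LLOQ line on the durability plots. Switching to the median does not help once more than half are censored, because it then equals LLOQ/2.

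Finally, the good Tobit results come from data simulated under its own model. In an illustrative mixture with 30% low responders sitting just below LLOQ, Tobit was 11–21% low and LLOQ/2 only 4–5% low. SAP 1 says that the Week 96 analysis will not be rerun, so replacing the estimator in the LTE would join two methods in one curve. This is a good reason to add Tobit rather than substitute it.

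**Conclusion.** The concern holds as a conditional risk to the LTE's main descriptive question. At SD 0.6 and n = 45, the planned geometric mean and CI can be trusted up to about 30% below LLOQ. From about half upward they cannot: 1.23-fold high with 80% coverage at 50%, and 1.65-fold high with almost no coverage at 70%. The exposure is greatest for the two ELISA antigens with LLOQ 625 and smaller for IgG1-4. Geometric mean increases use a higher floor and share the problem; their bias was not quantified here.

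The size rests on log-normal titres with a constant SD. The direction at 50% rests on an SD above about 0.38. Whether the problem occurs at all rests on an unreported share below LLOQ. Durability is exploratory and no hypothesis is tested, so what is at stake is interpretation, not error control. A safeguard is cheap and worth adding.

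**What to change.** For the LTE humoral outputs, in SAP 6.3 and 6.4:

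- Keep the LLOQ/2 geometric mean, for continuity with the Week 96 report.
- Add, as a sensitivity analysis, a left-censored (Tobit) geometric mean with 95% CI on log10 titre. Show it at all time points for the LTE set, so that each curve uses one estimator throughout.
- Print the percentage below LLOQ at each time point, and the LLOQ line, on every durability plot.
- Where about half or more of the values are below LLOQ, flag the substituted mean and base the durability statement on the share above LLOQ with its CI.
- While editing SAP 6.4, clarify the LOD exception for the gp140 ELISA: its LOD is listed as 0, and a value of 0 left unimputed has no log10.

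Cost: one extra standard analysis per assay and time point, and a log-normal tail assumption that should be stated with the results. If few values are below LLOQ, the two estimates should nearly agree and the conclusions should not change.

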## 6.5. Immune response assays: details

The details for each immune response assay are listed in following table. Final values of LLOQ/LOD might deviate from the table below, the dTA approved by the lab will be taken as source.

Assay	Test	Lab	Time Points	LLOQ	LOD	Unit	Responder definition (R)	Fold increase (FI) calculation
ELISA	AD26 VNA	Janssen Vaccines and Prevention	Wk0	17	NA	IC90	>LLOQ	NA
Env ELISA IgG-t gp140	Clade A (92UG037.1) Clade B (1990a) Clade C (Con C) Clade C (C97ZA.012)* Mos1	Janssen Vaccines and Prevention	Wk0 Wk 28 Wk 52 Wk78 Wk96	625 156.25 625 156.25 78.125	0	EU/ml	1) if baseline <LLOQ or missing, R>LLOQ 2) if baseline >=LLOQ, R=3-fold increase from baseline	1) if baseline >LLOQ, FI=Value post-baseline/Value wk0 2) if baseline<LLOQ, FI=value post-baseline/LLOQ
Env ELISA IgG1-4	Clade C (C97ZA.012) IgG1 Clade C (C97ZA.012) IgG2 Clade C (C97ZA.012) IgG3 Clade C (C97ZA.012) IgG4	BIDMC	Wk0 Wk 28 Wk 52 Wk78 Wk96	12.3 28.7 12.4 13.2	4	EC50		
Env ADCP gp140	Clade A (92UG037.1) Clade B (1990a) Clade C (Con C) Clade C (C97ZA.012)* Mos1	Ragon	Wk0 Wk 16 (n=72) Wk 28 Wk 52 Wk78 Wk96	NA	5.16 6.43 6.49 4.32 4.28	PS	1) if baseline <LOD, R>LOD 2) if baseline >=LOD, R=3-fold increase from baseline	1) if baseline >LOD, FI=Value post-baseline/Value wk0 2) if baseline<LOD, FI=value post-baseline/LOD
TZM-bl	Tier1 Clade C (MW965.26)	Duke U	Wk28 Wk52	20	NA	ID50	>LLOQ	NA
	Tier 2 Clade A (398F1) n Clade AC (246F3) n Ab Clade AE (CNE55) nAb Clade AE (CNE8) nAb Clade B (TRO11) nAb Clade B (X2278) nAb Clade BC (BBOX2000) nAb Clade BC (CH119) nAb		Wk28 (n=72)	10				

Assay	Test	Lab	Time Points	LLOQ	LOD	Unit	Responder definition (R)	Fold increase (FI) calculation
	Clade C ( Ce1176) nAb Clade C (25710) nAb Clade C (Ce0217 ) nAb Clade G (X1632) nAb							
BAMA IgG3	HIV ENV Con S gp140 CFI (Clade M) HIV ENV Con 6 gp120/B (Clade M) HIV ENV gp41 HIV ENV 1086C_D7gp120 (Clade C) HIV ENV 1086C gp140 (Clade C) HIV ENV 1086C_V1V2 (Clade C) HIV ENV gp70_B.CaseA_V1V2 (Clade B)	Duke U	Wk0 Wk 28 Wk 52 Wk78 Wk96	100 a	NA	MFI	BAMA interpretation= 1	1) if baseline >LLOQ, FI=Value post baseline/Value wk0 2) if baseline<LLOQ, FI=value post baseline/LLOQ
BAMA IgGA	Con S gp140 CFI Con 6 gp120/B gp41 1086C_D7gp120.avi/293F A1.con.env03 140 CF 00MSA 4076 gp140		Wk0 Wk 28 Wk 52 Wk78					
BAMA IgG1	Con S gp140 CFI Con 6 gp120/B gp41 1086C_D7gp120.avi/293F 1086C gp140C_avi C.1086C_V1_V2 Tags gp70_B.CaseA_V1_V2							

a This is not LLOQ but positivity cutoff as provided by the lab applied and is based on the 3 response call criteria which include the 95% of baseline responses per antigen

Assay	Test	Lab	Time Points	LLOQ	LOD	Unit	Responder definition (R)	Fold increase (FI) calculation
BAMA Breadth	HIV ENV gp120 Clade A (51802) IgG-t Ab Clade AE (254008) IgG-t Ab Clade AE (A244) IgG-t Ab Clade B (B.6240) IgG-t Ab Clade B (BORI) IgG-t Ab Clade B (TT31P) IgG-t Ab Clade BC (CNE20) IgG-t Ab Clade BC(BJOX002) IgG-t Ab Clade C(1086C_D7) IgG-t Ab B Clade M (Con 6) IgG-t Ab  HIV ENV gp140 Clade B (SC42261) IgG-t Ab Clade C (CH505TF) IgG-t Ab C Clade A (9004S) IgG-t Ab C Clade B (RHPA) IgG-t Ab C Clade B (WITO) IgG-t Ab C Clade C (1086C) IgG-t Ab C Clade C (BF1266) IgG-t Ab CF Clade AE (conAE) IgG-t Ab CFI Clade M(Con S) IgG-t Ab  HIV ENV gp41 IgG-t Ab  HIV ENV gp70 Clade A (191084) IgG-t Ab Clade AE (C2101) IgG-t Ab Clade AE (CM244) IgG-t Ab Clade B (62357.14) IgG-t Ab Clade B (CaseA) IgG-t Ab Clade B (RHPA4259) IgG-t Ab Clade B (TT31P) IgG-t Ab Clade B(700010058) IgG-t Ab Clade BC (BJOX) IgG-t Ab Clade C (96ZM651) IgG-t Ab Clade C (BF1266) IgG-t Ab		Wk0 Wk 28 Wk 52 Wk78 Wk96					

Assay	Test	Lab	Time Points	LLOQ	LOD	Unit	Responder definition (R)	Fold increase (FI) calculation
	Clade C (CAP210) IgG-t Ab Clade C(Ce1086) IgG-t Ab Clade C(TV1.21)IgG-t Ab Clade C (001428)IgG-t Ab Clade C (7060101641)IgG-t Ab							
BAMA IgG2	HIV ENV gp41 IgG2 Ab HIV ENV gp70 Clade C (Ce1086) IgG2 Ab HIV ENV gp70 Clade B (CaseA) IgG2 Ab HIV ENV gp140CFI Clade M (Con S) IgG2 Ab HIV ENV gp140 Clade C (1086C) IgG2 Ab HIV ENV gp120/B Clade M (Con 6) IgG2 Ab HIV ENV gp120 Clade C (1086C_D7) IgG2 Ab		Wk0 Wk 28					
BAMA IgG4	HIV ENV gp70 Clade C (Ce1086) IgG4 Ab HIV ENV gp70 Clade B (CaseA) IgG4 Ab HIV ENV gp41 IgG4 Ab HIV ENV gp140CFI Clade M (Con S) IgG4 Ab HIV ENV gp140 Clade C (1086C) IgG4 Ab HIV ENV gp120/B Clade M (Con 6) IgG4 Ab HIV ENV gp120 Clade C (1086C_D7) IgG4 Ab		Wk0 Wk 28					
ELISpot	Env peptide pool Mos1 Pol peptide pool Mos1 Gag peptide pool Mos1 Env peptide pool Mos2	BIDMC	Wk0 Wk26 Wk 50 Wk78	55	0	SFC/10  PBMC	1) if baseline <threshold, R>threshold 2) if baseline	73 b 112 87 70
							NA	

Assay	Test	Lab	Time Points	LLOQ	LOD	Unit	Responder definition (R)	Fold increase (FI) calculation
	Pol peptide pool Mos2 Gag peptide pool Mos2 Env peptide pool PTE a (Env peptide pool 1 PTE, Env peptide pool 2 PTE, Env peptide pool 3 PTE) Pol peptide pool PTE Gag peptide pool PTE		Wk96				>=threshold, R=3-fold increase from baseline	63 55 100 105 181
ICS (CD4+, CD8+)	Combined pools HIV Gag pep pool (Mos1) HIV Pol pep pool (Mos1) HIV ENV pep pool (Mos1) HIV ENV pep pool clade C (C97ZA.012) HIV ENV pep pool (Clinical PTE) Separated pools HIV Pol RT pep pool (Mos1)* HIV Pol RNaseInt pep pool 1 (Mos1) HIV ENV gp120 pep pool 1 (Mos1)* HIV ENV gp41 pep pool 1 (Mos1) HIV ENV gp120 pep pool clade C (C97ZA.012) HIV ENV gp41 pep pool clade C (C97ZA.012) HIV ENV pep pool 1 (Clinical PTE) a	FHCRC	Wk26 Wk 50 Wk78 Wk96	NA	NA	% of CD4+/CD8+ T cells	ICS interpretation=1	NA

a ENV pep pool (PTE) will be provided split in pool 1,2,3: for the purpose of the Week 28 PA they will be reported only as sum of the 3: HIV ENV pep pool. The ADAM should however contain also the 3 separated pools.

b Threshold for ELISpot test is based on the 95 percentile from the baseline values of about 350 subjects on that test in the HIV-V-A004 study

Assay	Test	Lab	Time Points	LLOQ	LOD	Unit	Responder definition (R)	Fold increase (FI) calculation
	HIV ENV pep pool 2 (Clinical PTE) a HIV ENV pep pool 3 (Clinical PTE) a							

NA: not applicable; PS: phagocytic score; SFC: spot forming cells, PBMC: peripheral blood mononuclear cell, MFI: median fluorescent intensities

\* Clade C (C97ZA.012) for Elisa and ADCP, ENV gp120 Mos1 and Pol RT Mos1 for ICS will be available for group 1 at additional intermediate timepoints: exploratory scatterplots with timepoint on the x-axis will be provided.

---

a ENV pep pool 1,2,3 (PTE Clinical): calculation of the pure cytokine count cannot be obtained from the combined HIV ENV pep pool (only Boolean OR data will be available) so it will be derived from the 3 separated pools.

**7. VISP**

VISP data was collected throughout the study outside of the EDC database. An overview of the results (Reactive, Indeterminate, Not Reactive) of the HIV Ag/Ab Combo 4th generation assays will be provided by visit and by brand name.

**8. SOCIAL IMPACT QUESTIONNAIRE**

Data from the Vaccine Research Center (VRC) Social Impact Questionnaire will be listed and summarized using descriptive statistics.

## APPENDIX 1: LABORATORY, VITAL SIGNS AND ECG ABNORMALITY GRADINGS

PARAMETER	LABORATORY a			
	GRADE 1 MILD	GRADE 2 MODERATE	GRADE 3 SEVERE	GRADE 4 POTENTIALLY LIFE-THREATENING
HEMATOLOGY				
Absolute Neutrophil Count (ANC) c	1.000 x 10  – 1.300 x 10  /L	0.750 x 10  – 0.999 x 10  /L	0.500 x 10  – 0.749 x 10  /L	<0.500 x 10  /L
Hemoglobin (Hgb) (HIV NEGATIVE ONLY)	10.0 – 10.9 g/dL or Any decrease b 2.5 – 3.4 g/dL	9.0 – 9.9 g/dL or Any decrease b 3.5 – 4.4 g/dL	7.0 – 8.9 g/dL or Any decrease b ≥ 4.5 g/dL	<7.0 g/dL
Platelets, decreased	100.000 x 10  – 124.999 x 10  /L	50.000 x 10  – 99.999 x 10  /L	25.000 x 10  – 49.999 x 10  /L	<25.000 x 10  /L
WBC, decreased	2.000 x 10  – 2.500 x 10  /L	1.500 x 10  – 1.999 x 10  /L	1.000 x 10  – 1.499 x 10  /L	<1.000 x 10  /L
CHEMISTRIES				
ALT (SGPT)	1.25 – 2.5 x ULN	2.6 – 5.0 x ULN	5.1 – 10.0 x ULN	>10.0 x ULN
AST (SGOT)	1.25 – 2.5 x ULN	2.6 – 5.0 x ULN	5.1 – 10.0 x ULN	>10.0 x ULN
Creatinine	1.1 – 1.3 x ULN	1.4 – 1.8 x ULN	1.9 – 3.4 x ULN	≥ 3.5 x ULN
URINALYSIS				
Hematuria	6-10 RBV/HPF	>10 RBV/HPF	Gross, with or without clots or with RBC casts	Transfusion indicated
Proteinuria, random collection	1+	2-3+	4+	NA

a This list is restricted to the laboratory parameters collected in this study for which a DAIDS grading is available. Only ranges applicable for adults are reported. For a complete list refer to the CTP appendix 1

b The decrease is a decrease from baseline

c If ANC is not available the values will be derived by from the ratio Neutrophils/Leucocytes

VITAL SIGNS AND ECG					
PARAMETER	UNIT	GRADE 1	GRADE 2	GRADE 3	GRADE 4
Temperature b	°C	≥38.0 - ≤38.4	≥38.5 - ≤38.9	≥39.0 - ≤40.0	>40.0
Hypertensionb					
Systolic Blood Pressure	mmHg	≥140 - ≤159	≥160 - ≤179	≥180	NA
Diastolic Blood Pressure	mmHg	≥90 - ≤99	≥100 - ≤109	≥110	NA
Hypotension	mmHg	NA	NA	NA	NA
Pulse rate					
Tachycardia	bpm	≥101-≤115	≥116 - ≤130	>130	NA
Bradycardia	bpm	≥50 - ≤54	≥45 - ≤49	<45	NA
QTc ab	msec	≥450 - ≤ 470 or increase ≤30 from baseline	>470 - ≤ 490 or increase >30 and ≤50 from baseline	>490 or increase >50 from baseline	NA
PR b	msec	≥210 - ≤ 250	>250	NA	NA

aAccording to Bazett's or Fridericia's formula

b DAIDS grading, see also CTP appendix 1
